 - Within 8 weeks before the first administration of study drug, has a negative interferon gamma release assays (IGRAs) result, or have a newly identified positive IGRAs result ([Attachment 9](#)) in which active TB has been ruled out and for which appropriate treatment for latent TB ([Attachment 9](#)) has been initiated at least 3 weeks before the first administration of study drug. A subject whose first IGRA result is indeterminate should have the test repeated. In the event that the second IGRA result is also indeterminate, the subject should be excluded from the study.
- Note : The IGRA and the tuberculin skin test are not required at screening for subjects with a history of latent TB and ongoing treatment for latent TB or documentation of having completed adequate treatment as described above; subjects with documentation of having completed adequate treatment as described above are not required to initiate additional treatment for latent TB.
- Has a chest radiograph (posterior-anterior and lateral views, or substitutable with chest computed tomography [CT]), taken within 12 weeks before the first administration of study drug and read by a qualified radiologist or pulmonologist, with no evidence of current, active TB or old, inactive TB.
11. Agrees not to receive a live virus or live bacterial vaccination during the study, or within 12 weeks after the last administration of study drug. For information on Bacille Calmette-Guérin (BCG) vaccination, see Inclusion Criterion 12.
12. Agrees not to receive a BCG vaccination during the study, or within 52 weeks after the last

administration of study drug.

13. Has screening laboratory test results within the following parameters, if one or more of the laboratory parameters is out of range, a single retest of laboratory values is permitted:
- Hemoglobin ≥ 10 g/dL (SI: ≥ 100 g/L)
 - White blood cells $\geq 3.5 \times 10^3/\mu\text{L}$ (SI: ≥ 3.5 GI/L)
 - Neutrophils $\geq 1.5 \times 10^3/\mu\text{L}$ (SI: ≥ 1.5 GI/L)
 - Platelets $\geq 100 \times 10^3/\mu\text{L}$ (SI: ≥ 100 GI/L)
 - Serum creatinine ≤ 1.5 mg/dL (SI: ≤ 129 $\mu\text{mol/L}$)
- Aspartate aminotransferase (AST), alanine aminotransferase (ALT), and alkaline phosphatase levels must be $\leq 2 \times$ upper limit of normal (ULN) for the laboratory conducting the test.
14. Agrees to avoid prolonged sun exposure and avoid use of tanning booths or other ultraviolet (UV) light sources to the palms and soles during study.

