4.3. Prohibitions and Restrictions

Potential subjects must be willing and able to adhere to the following prohibitions and restrictions during the course of the study to be eligible for participation:

1. If a woman of childbearing potential is heterosexually active, she must remain on a highly effective method of birth control (see inclusion criteria 6) during the study and for 12 weeks after receiving the last dose of any study agent.

2. If a man who has not had a vasectomy and is sexually active with a woman of childbearing potential must use a barrier method of birth control, eg, either condom with spermicidal foam/gel/film/cream/suppository or partner with occlusive cap (diaphragm or cervical/vault caps) with spermicidal foam/gel/film/cream/suppository, and all men must also not donate sperm during the study and for 12 weeks after receiving the last dose of study drug.
3. Must agree not to receive a live virus or bacterial vaccination during the study or up to 12 weeks after the last administration of any study agent.
4. Must agree not to receive a BCG vaccination during the study or up to 52 weeks after the last administration of any study agent.
5. Must comply with restrictions on prestudy and concomitant medications (see Section 8).
6. Must avoid prolonged sun exposure and avoid use of tanning booths or other UV light sources to the palms and soles during study.
7. Must agree that every effort should be made to stop smoking.
8. Must agree not to participate in other clinical study which will collect the skin biopsy samples during the study and for 12 weeks after receiving the last dose of any study agent.

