6. DOSAGE AND ADMINISTRATION

A 100 mg/mL solution of CNTO 1959 in a single-use prefilled syringe (PFS) assembled with the UltraSafe PLUS™ Passive Needle Guard (PFS-U) device will be used. Liquid placebo for CNTO 1959 will also be supplied as a PFS assembled with the PFS-U. During the study, all subjects will subcutaneously receive two syringes for each dose.

All study drug administrations will be given at the study site. The dose regimens are as follows:

- **Group I:** Two syringes of CNTO 1959 100 mg at Weeks 0, 4, 12 and q8w thereafter through Week 60, 2 syringes of placebo for CNTO 1959 100 mg at Week 16 to maintain the blind.
- **Group II:** A syringe of CNTO 1959 100 mg and a syringe of placebo for CNTO 1959 100 mg at Weeks 0, 4, 12 and q8w thereafter through Week 60, 2 syringes of placebo for CNTO 1959 100 mg at Week 16 to maintain the blind.
- **Group III:** Two syringes of placebo for CNTO 1959 100 mg at Weeks 0, 4 and 12 to maintain the blind. At Week 16, placebo subjects will be randomized in a 1:1 ratio to CNTO 1959 200 mg arm (Group IIIa) or 100 mg arm (Group IIIb). Group IIIa subjects will receive 2 syringes of CNTO 1959 100 mg at Weeks 16, 20 and q8w thereafter through Week 60. Group IIIb subjects will receive a syringe of CNTO 1959 100 mg and a syringe of placebo for CNTO 1959 100 mg at Weeks 16, 20 and q8w thereafter through Week 60.

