8. CONCOMITANT THERAPY

Any concomitant therapy that could affect palmoplantar pustulosis or the efficacy evaluation and would be used for serious adverse events must be recorded throughout the study from screening until the study end. Other concomitant therapies must be recorded throughout the study from screening and continuing until 12 weeks after the last dose of study drug for randomized subjects.

All therapies (prescription or over-the-counter medications, including vaccines, vitamins, herbal supplements) different from the study drug must be recorded in the eCRF. Modification of an effective preexisting therapy should not be made for the explicit purpose of entering a subject into the study.

8.1. Week 0 through Week 60

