8.1.2. Concomitant Medications for Conditions Other than Palmoplantar Pustulosis

Every effort should be made to keep subjects on stable concomitant medications. If the medication is temporarily discontinued because of abnormal laboratory values, side effects, concurrent illness, or the performance of a procedure, the change and reason for it should be clearly documented in the subject's medical record.

The use of nonsteroidal anti-inflammatory drugs is allowed. However, disease-modifying agents such as MTX, sulfasalazine, or IM gold are prohibited during the study. Antimalarial agents, with the exception of chloroquine, may be used after Week 60.

The use of corticosteroids for indications other than palmoplantar pustulosis should be limited to situations for which, in the opinion of the treating physician, there are no adequate alternatives. They should be used on a short-term basis, preferably for ≤ 2 weeks. Longer-term use of corticosteroids should be discussed with the medical monitor or designee and may require discontinuation of study drug. Topical medication to body area other than palms and soles, inhaled, otic, ocular, nasal or other routes of mucosal delivery of corticosteroids are allowed throughout the study.

8.2. After the week 60

After the Week 60 visit, there is no limitation on concomitant therapies.

The sponsor must be notified in advance (or as soon as possible thereafter) of any instances in which prohibited therapies are administered.

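### Section 8.2 lifts all limits on concomitant therapies after Week 60 without saying whether the live-vaccine and BCG restrictions, whose post-dose windows start at that visit, still apply

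*Protocol*

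**What the plan says.** Four places in the Protocol bear on vaccination after the last dose.

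- **Section 4.1, Inclusion Criteria 11 and 12.** The subject "Agrees not to receive a live virus or live bacterial vaccination during the study, or within 12 weeks after the last administration" of study drug, and separately "Agrees not to receive a BCG vaccination during the study, or within 52 weeks after the last" administration.
- **Section 4.3, Prohibitions and Restrictions, items 3 and 4.** The same restrictions appear as rules for the course of the study: "Must agree not to receive a live virus or bacterial vaccination during the study or up to 12 weeks after the last administration", and "Must agree not to receive a BCG vaccination during the study or up to 52 weeks after the last administration of any study agent".
- **Section 8, Concomitant Therapy.** The recording rule counts vaccines as therapies: "All therapies (prescription or over-the-counter medications, including vaccines, vitamins, herbal supplements) different from the study drug must be recorded in the eCRF".
- **Section 8.2, After the week 60.** "After the Week 60 visit, there is no limitation on concomitant therapies". The sentence that follows asks sites to tell the sponsor when prohibited therapies are given, but does not say which therapies are still prohibited at that stage.

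Section 6 fixes the last dose. Groups I and II receive CNTO 1959 "at Weeks 0, 4, 12 and q8w thereafter through Week 60", and Group III's schedule also ends at Week 60. Section 3.1 describes an observational period without study drug from Week 60 to Week 84.

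**The concern.** Sections 4.1 and 4.3 restrict live and BCG vaccines for set periods counted from the last dose. Section 8.2 removes limits on concomitant therapies from the visit at which that last dose is given. Vaccines are named as therapies at the head of Section 8, above both 8.1 and 8.2, so on its face Section 8.2 reaches them.

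Item 5 of Section 4.3 sends the reader to Section 8 for restrictions on prestudy and concomitant medication. Section 8 contains no vaccine restriction and no pointer back to Section 4.3. Someone checking the therapy section during follow-up would find only the unqualified sentence in 8.2.

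What is at stake is a safety restriction on subjects and the consistency of instructions across sites. Two sites could read the same document and answer the same vaccine question differently.

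**Working it through.** This is calendar arithmetic and a comparison of text. No power, alpha or sample size figure is involved.

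**Last dose.** Groups I and II are dosed every 8 weeks from Week 12: 12 + 6 × 8 = Week 60. Group III is dosed every 8 weeks from Week 20: 20 + 5 × 8 = Week 60.

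**The protocol's own figure.** Section 12.3.1 equates 12 weeks after the last dose with the Week 72 visit. 60 + 12 = 72, so this reproduces.

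**Windows for a subject who completes dosing.**

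| Restriction | Runs to | Weeks after Week 60 |
|---|---|---|
| Live vaccine, 12-week limb | 60 + 12 = Week 72 | 12 |
| Live vaccine, during-the-study limb | Week 84 (subject's own last visit) | 84 − 60 = 24 |
| BCG, 52-week limb | 60 + 52 = Week 112 | 52, of which 24 are before Week 84 and 112 − 84 = 28 after it |

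For these subjects the whole of each post-dose window lies in the period that Section 8.2 describes as free of limits.

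**Subjects who stop dosing early.** The vaccine windows count from the last dose, but Section 8.2 counts from the Week 60 visit, so the overlap differs. With a last dose at Week 44 the 12-week limb ends at 44 + 12 = Week 56, before 8.2 applies. With a last dose at Week 52 it ends at 52 + 12 = Week 64, partly inside. The figures in the table therefore hold for completers only.

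**Does the text limit the scope of 8.2?**

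1. It refers to concomitant therapies in general, not to the limits in 8.1.
2. It makes no exception for vaccines and does not refer to 4.1 or 4.3.
3. Its next sentence suggests that some therapies may remain prohibited but does not name them.
4. Section 8.1.2 allows antimalarials other than chloroquine after Week 60. That implies a limit on chloroquine that outlasts Week 60, which 8.2 read literally denies. Vaccines are therefore not the only place where the breadth of 8.2 causes difficulty.

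**The case against.** The best answer is that Section 8.2 is simply the counterpart of Section 8.1. The headings pair the period up to Week 60 with the period after it. Section 8.1 covers topical, focal-infection, phototherapy, systemic, PAO and other-condition treatments and never mentions vaccines. Section 4.3 lists the vaccine restrictions (items 3 and 4) apart from compliance with Section 8 (item 5), so ending the Section 8 limits would end item 5 only. A specific rule normally qualifies a general one, and reading 8.2 literally would empty the post-dose windows for every subject who completes dosing. The mention of vaccines in Section 8 is also a recording instruction, not a definition of what 8.2 permits.

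Much of this stands. It makes the narrow reading of 8.2 plausible, and a careful site might well adopt it. It also means that a clause confining 8.2 to the 8.1 limits would resolve the vaccine question. But the narrow reading has to be inferred. Section 8.2 does not state it, and the unexplained reference to prohibited therapies leaves its scope open.

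A reader might infer more: that the protocol tells sites to give live vaccines after Week 60, or cancels the vaccine restrictions outright. The documents do not support that. Section 8.2 at most permits, and the restrictions remain in four explicit places. Nor should a residual drug level be attached to the overlap using the Phase 1 half-life alone. Section 1.1 describes slow absorption with a median time to peak of about 3 to 6 days after a single injection, so a simple decline from the day of dosing does not describe the early weeks.

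**Conclusion.** The point holds as an internal inconsistency. Read as written, Section 8.2 conflicts with Inclusion Criteria 11 and 12 and Section 4.3, items 3 and 4. For subjects who complete dosing the conflict covers Weeks 60 to 72 for live vaccines, or to Week 84 under the during-the-study wording, and Weeks 60 to 112 for BCG.

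This rests on the last dose being given at Week 60 as scheduled, and on taking a subject's own Week 84 visit as the end of the study for that subject. The practical reach is narrow: only a subject offered a live or BCG vaccine after Week 60 is affected, and the documents give no figure for how often that would happen. No endpoint, error rate or power statement is touched, and the Week 16 primary analysis is unaffected. It merits correction because it concerns a safety restriction and the repair is small.

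**What to change.** Reconcile Section 8.2 with Inclusion Criteria 11 and 12 and Section 4.3, items 3 and 4. Section 8.2 should state which restrictions it lifts and whether the live-vaccine and BCG restrictions continue after Week 60, with a cross-reference to Section 4.3. It should also say which therapies its notification sentence still covers. Live vaccines and BCG have different windows, so the aim is agreement across passages for each vaccine type, not one common end date. Which rule stands is for the sponsor's medical team to decide.

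The cost is one clause at the next amendment. A site letter could explain the intended reading in the meantime, but Section 17.1 requires a formal amendment for any change to the protocol itself. No visits, procedures, subjects or analyses are added.

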4.2. Exclusion Criteria

Any potential subject who meets any of the following criteria will be excluded from participating in the study. The subject will be excluded if he or she:

1. Has a diagnosis of plaque-type psoriasis.
2. Has obvious improvement during screening (≥ 5 PPPASI total score improvement during the screening).
3. Has a history or current signs or symptoms of severe, progressive, or uncontrolled renal, cardiac, vascular, pulmonary, gastrointestinal, endocrine, neurologic, hematologic, rheumatologic, psychiatric, or metabolic disturbances.
4. Has unstable cardiovascular disease, defined as a recent clinical deterioration (eg, unstable angina, rapid atrial fibrillation) in the last 12 weeks or a cardiac hospitalization within the last 12 weeks before screening.
5. Currently has a malignancy or has a history of malignancy within 5 years before screening (with the exception of a nonmelanoma skin cancer that has been adequately treated with no

evidence of recurrence for at least 12 weeks before screening or cervical carcinoma in situ that has been treated with no evidence of recurrence for at least 12 weeks before screening).

6. Has a history of lymphoproliferative disease, including lymphoma; a history of monoclonal gammopathy of undetermined significance (MGUS); or signs and symptoms suggestive of possible lymphoproliferative disease, such as lymphadenopathy or splenomegaly.
7. Has a history of chronic or recurrent infectious disease, including but not limited to chronic renal infection, chronic chest infection (eg, bronchiectasis), recurrent urinary tract infection (recurrent pyelonephritis or chronic nonremitting cystitis), fungal infection (mucocutaneous candidiasis), or open, draining, or infected skin wounds or ulcers.
8. Has or has had a serious infection (eg, sepsis, pneumonia or pyelonephritis) , or has been hospitalized or received IV antibiotics for an infection during the 8 weeks before screening.
9. Has a history of active granulomatous infection, including histoplasmosis or coccidioidomycosis, before screening. Refer to Inclusion Criterion 10 for information regarding eligibility with a history of latent TB.
10. Has a chest radiograph within 12 weeks before the first administration of study drug that shows an abnormality suggestive of a malignancy or current active infection, including TB.
11. Has persistently indeterminate (indeterminate on repeat sampling) IGRA results.
12. Has ever had a nontuberculous mycobacterial infection or opportunistic infection (eg, cytomegalovirus, pneumocystosis, aspergillosis).
13. Has a history of an infected joint prosthesis, or has received antibiotics for a suspected infection of a joint prosthesis, if that prosthesis has not been removed or replaced.
14. Has or has had herpes zoster within the 8 weeks before screening.
15. Is infected with human immunodeficiency virus (HIV, positive serology for HIV infection) or human T-lymphotropic virus-1 (HTLV-1, positive serology for HTLV-1 infection).
16. Tests positive for hepatitis B virus (HBV) infection or who are seropositive for antibodies to hepatitis C virus (HCV) at screening ([Attachment 10](#)).
17. Has a transplanted organ (with exception of a corneal transplant >12 weeks before the first administration of study drug).
18. Subject has had major surgery, (eg, requiring general anesthesia) within 8 weeks before screening, or will not have fully recovered from surgery, or has surgery planned during the time the subject is expected to participate in the study (52 weeks).

Note: subjects with planned surgical procedures to be conducted under local anesthesia

may participate.

19. Has current drug-induced palmoplantar pustulosis (eg, a new onset of palmoplantar pustulosis or an exacerbation of palmoplantar pustulosis from beta blockers, calcium channel blockers, lithium, or biologic therapy including infliximab, adalimumab or etanercept etc.).
20. Is pregnant, nursing, or planning a pregnancy (both men and women) within 20 weeks following the last administration of study drug.
21. Has previously received CNTO 1959.
22. Has received focal infection treatment (e.g., tonsillectomy and dental therapy) within 24 weeks of the first administration of any study agent.
23. Has received any anti-TNF α biologic therapy within 12 weeks or 5 half-lives of the first administration of study drug, whichever is longer.
24. Has received any therapeutic agent directly targeted to IL-12, IL-17, or IL-23 within 24 weeks of the first administration of study drug (including but not limited to tocilizumab, ustekinumab, tildrakizumab [MK3222], secukinumab [AIN457], ixekizumab [LY2439821], or brodalumab [AMG 827]).
25. Has received natalizumab, belimumab, or agents that modulate B cells or T cells (eg, rituximab, alemtuzumab, abatacept, or visilizumab) within 52 weeks of the first administration of study drug.
26. Has received phototherapy or any systemic medications/treatments that could affect palmoplantar pustulosis or efficacy evaluations (including, but not limited to, oral or injectable corticosteroids, retinoids, 1,25-dihydroxy vitamin D3 and analogues, psoralens, sulfasalazine, hydroxyurea, fumaric acid derivatives, herbal treatments, or traditional Taiwanese, Korean, or Chinese medicines) within 4 weeks of the first administration of study drug.
27. Has used topical medications/treatments that could affect palmoplantar pustulosis or efficacy evaluations (including, but not limited to, corticosteroids, vitamin D3 derivatives, tacrolimus, and antibiotics) within 2 weeks of the first administration of study drug.
28. Has received any systemic medications/treatments that could affect pustulotic arthro-osteitis or efficacy evaluation of pustulotic arthro-osteitis (eg, bisphosphonates, immunosuppressants [eg, methotrexate, azathioprine, cyclosporine, 6-thioguanine, mercaptopurine, mycophenolate mofetil, tacrolimus]) or anakinra within 4 weeks of the first administration of study drug.
29. Is currently receiving lithium, antimalarials, or intramuscular (IM) gold, or have received

lithium, antimalarials, or IM gold within 4 weeks of the first administration of study drug.

30. Has received an experimental antibody or biologic therapy within the previous 24 weeks, or received any other experimental therapy or new investigational agent within 30 days or 5 half-lives (whichever is longer) of any study drug administration or is currently enrolled in another study using an investigational agent or procedure.
31. Has known intolerance or hypersensitivity to any biologic medication, or known allergies or clinically significant reactions to murine, chimeric, or human proteins, mAbs, or antibody fragments.
32. Has known allergies, hypersensitivity, or intolerance to CNTO 1959 or its excipients (refer to Investigator's Brochure).
33. Has received, or is expected to receive, any live virus or bacterial vaccination within 12 weeks before the first administration of study drug. For BCG vaccine, see Exclusion Criterion 35.
34. Has had a BCG vaccination within 52 weeks of screening.
35. Is known to have had a substance abuse (drug or alcohol) problem within the previous 52 weeks before screening.
36. Is unable or unwilling to undergo multiple venipunctures because of poor tolerability or lack of easy access to veins.
37. Lives in an institution on court or authority order.
38. Has any condition that, in the opinion of the investigator, would make participation not be in the best interest (eg, compromise the well-being) of the subject or that could prevent, limit, or confound the protocol-specified assessments.

Note : Investigators should ensure that all study enrollment criteria have been met at screening. If a subject's status changes (including laboratory results or receipt of additional medical records) after screening but before the first dose of study drug is given such that he or she no longer meets all eligibility criteria, then the subject should be excluded from participation in the study.

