Inclusion/exclusion criteria	X	X																	
Study Drug Administration																			
Randomization		X					X												
Study agent administration		X		X		X	X	X		X		X		X		X	X		
Safety Assessments																			
Physical examination	X	X	X	X	X	X	X	X	X	X	X	X	X	X	X	X	X	X	X
Vital signs ^d	X	X	X	X	X	X	X	X	X	X	X	X	X	X	X	X	X	X	X
Height		X																	
Weight		X					X									X		X	
12-lead ECG	X						X									X		X	
Chest radiograph (Chest CT or Chest X-ray: both posterior-anterior and lateral views)	X						X									X		X	
Urine pregnancy test ^e		X		X		X	X	X		X		X		X		X	X	X	
Efficacy Assessments																			
PPPASI	X	X	X	X	X	X	X	X	X	X	X	X	X	X	X	X	X	X	X
PPSI	X	X	X	X	X	X	X	X	X	X	X	X	X	X	X	X	X	X	X
PGA	X	X	X	X	X	X	X	X	X	X	X	X	X	X	X	X	X	X	X
DLQI ^f		X					X				X					X		X	X

Phase Week	Screening ^a	Treatment Period																Observational Period	
		0	2	4	8	12	16	20	24	28	32	36	40	44	48	52	60	72(ET ^b)	84
Allowance (day)			±3	±3	±7	±7	±7	±7	±7	±7	±7	±7	±7	±7	±7	±7	±7	±7	±7
Study Procedures^c																			
SF-36 ^f		X					X				X					X		X	X
EQ-5D ^f		X					X				X					X		X	X
MRI ^g		X ^g														X			
Photographs ^h	X	X					X				X					X		X	X
Clinical Laboratory Assessments^{i,j}																			
Hematology	X	X	X	X	X	X	X	X	X	X		X		X		X		X	
Chemistry	X	X	X	X	X	X	X	X	X	X		X		X		X		X	
Lipid panel ^l		X																	
Serology / other screening	X																		
Pharmacokinetics / Immunogenicity^k																			
Serum sample collection for PK		X		X	X	X	X	X	X	X		X		X	X	X	X	X	
Serum sample collection for population PK							← X ^l →												
Serum sample collection for immunogenicity		X		X			X								X	X	X	X	
Biomarkers																			
Serum sample collection		X					X								X		X	X	
Ongoing Subject Review																			
Smoking status	X	X	X-----X																
Concomitant therapy	X	X	X-----X																
Tuberculosis evaluation	X	X	X-----X																
Adverse events ^m	X	X	X-----X																

Footnotes

- a. The screening period is planned to allow approximately 6 weeks.
- b. ET: Early Termination. For subjects who withdraw from study participation, every effort should be made to conduct final efficacy and safety assessments which are listed in Week72.

- c. All study procedures and evaluations are to be completed before study drug injection.
- d. Axillary temperature, Pulse rate, Blood pressure

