3. STUDY DESIGN AND RATIONALE

3.1. Overview of Study Design

This is a Phase 3, randomized, double-blind, multicenter placebo-controlled study in subjects with palmoplantar pustulosis. The target population is adult men or women, with a diagnosis of palmoplantar pustulosis (with or without PAO) for at least 24 weeks before screening. Subjects must have a PPPASI total score ≥ 12 and a PPPASI severity score of pustules/vesicle on the

palms or soles ≥ 2 at screening and baseline. Subjects must have inadequate response to conventional therapies (topical treatment, and/or phototherapy, and/or systemic treatment).

Subjects with drug-induced palmoplantar pustulosis (eg, a new onset of palmoplantar pustulosis or an exacerbation of palmoplantar pustulosis from beta blockers, calcium channel blockers, or lithium, or biologic therapy etc.) are excluded. Subjects who have ever received CNTO 1959 are also excluded.

This study will be conducted using an adaptive statistical design permitting one interim analysis and the potential to stop the study for futility and increase sample size for the final analysis with a maximum allowable sample size of 225 patients.

Key features of study drug administration for each treatment group are outlined below; for details regarding concomitant placebo administrations to maintain the blind, please see Section 6, Dosage and Administration.

Week 0 through Week 60 (Blinded Treatment Period)

As depicted in [Figure 1](#), approximately 150-225 subjects who satisfy all inclusion and exclusion criteria will be randomized in a 1:1:1 ratio to one of three arms:

- **Group I** (n = 50, max75): CNTO 1959 200 mg at Weeks 0, 4, 12 and q8w thereafter through Week 60.
- **Group II** (n = 50, max75): CNTO 1959 100 mg at Weeks 0, 4, 12 and q8w thereafter through Week 60.
- **Group III** (n = 50, max75): Placebo at Weeks 0, 4, and 12. Beginning at Week 16, subjects will be randomized in a 1:1 ratio to CNTO1959 200 mg arm (Group IIIa) or 100 mg arm (Group IIIb), and will receive the assigned dose of CNTO 1959 at Weeks 16, 20 and q8w thereafter through Week 60.

Subject will be assigned to 1 of 3 treatment groups using a stratified block randomization method in a 1:1:1 ratio at Week 0 and Group III subjects will be allocated in a 1:1 ratio to 1 of 2 treatment groups at Week 16. Stratification factors will be PPPASI total score range (≤ 20 score, 21-30 score, ≥ 31 score) and smoking status (smoking or non-smoking).

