After Week 60 until Week 84 (Observational Period)

[figure not shown]
The observational period will begin from Week 60 and extend until Week 84. All subjects will no longer receive the study drug during the observational period. Efficacy and safety will be evaluated at Week 72, and the durability of clinical response and safety at Week 84.

The investigators and subjects will be unblinded after the last subject has completed the Week 60 visit. The end of the study is defined as the time when the last subject completes the Week 84 visit. Database locks will occur at Weeks 16, 24, 52 and 84. Additional DBLs may also occur after Week 52 DBL during the study.

A serum sample for biomarkers will be collected from all subjects.

A diagram of the study design is provided below in [Figure 1](#). When approximately 40% of the 150 randomized subjects have completed Week 16 visit or have ended study participation before Week 16 visit, an interim analysis is planned to be conducted to re-estimate the sample size and determine whether to stop the study early for futility. An Independent Data Monitoring Committee (IDMC) will be constituted for safety monitoring and interim analysis review of this study.

Figure 1: Study design

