10. SUBJECT COMPLETION/WITHDRAWAL

10.1. Completion

A subject will be considered to have completed the study if he or she has completed assessments at Week 60 of the treatment phase. Subjects who prematurely discontinue study treatment for any reason before completion of the treatment phase will not be considered to have completed the study.

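### Exclusion criterion 18 gives expected participation as 52 weeks, which contradicts its own wording and a schedule with completion at Week 60 and the last visit at Week 84

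*Protocol*

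**What the plan says.** Criterion 18 in section 4.2 has three limbs: recent major surgery, incomplete recovery from surgery, and surgery planned for the period of the study. The third limb defines that period as "the time the subject is expected to participate in the study (52 weeks"). A note exempts "subjects with planned surgical procedures to be conducted under local anesthesia".

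Section 3.1 sets out a longer course:

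- The treatment period is headed "Week 0 through Week 60 (Blinded Treatment Period").
- Group I receives "CNTO 1959 200 mg at Weeks 0, 4, 12 and q8w thereafter through Week 60". Group II has the same timing, and Group III receives active drug from Week 16 through Week 60.
- "The observational period will begin from Week 60 and extend until Week 84".
- "The end of the study is defined as the time when the last subject completes the Week 84 visit".

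Section 10.1 defines completion for the individual subject: "A subject will be considered to have completed the study if he or she has completed assessments at Week 60 of the treatment phase". Footnote a of the Time and Events Schedule adds time before Week 0: "The screening period is planned to allow approximately 6 weeks".

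**The concern.** The criterion sets its window by expected participation and then gives that duration as a number the schedule does not support. An eligibility criterion is applied subject by subject, often by staff who work from the figure. Two sites could therefore decide the same subject differently, one following the words and the other the number.

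What is at stake lies late in the study. Surgery planned after Week 52 could coincide with the Week 60 dose, or with the Week 60, 72 and 84 assessments. Those visits serve the durability objective (section 2.1) and, up to Week 72, the safety summary (section 11.7).

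Two other sections touch the same ground. Section 8.1.1.2 does not permit focal infection treatment such as tonsillectomy at any time during the study, yet criterion 18 read by its number would not screen out such an operation planned for, say, Week 56. Section 12.3.2 exempts hospitalization for surgery planned before study entry from SAE reporting, so an admission of this kind need not appear as an SAE.

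**Working it through.** **Inputs, all from the protocol.** Stated participation: 52 weeks (4.2, criterion 18). Last dose: Week 60 (3.1). Completion: Week 60 assessments (10.1). Safety and efficacy visit: Week 72 (3.1). Last visit: Week 84 (3.1). Screening: about 6 weeks (Time and Events Schedule, footnote a).

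**Can 52 weeks be reproduced?** Span = end week − start week, with screening placed at Week −6:

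| Span | Weeks | Minus 52 |
|---|---|---|
| Week 0 to last dose and completion | 60 − 0 = 60 | 8 |
| Week 0 to Week 72 visit | 72 − 0 = 72 | 20 |
| Week 0 to Week 84 visit | 84 − 0 = 84 | 32 |
| Screening to Week 60 | 60 + 6 = 66 | 14 |
| Screening to Week 84 | 84 + 6 = 90 | 38 |
| Active treatment, Group III | 60 − 16 = 44 | −8 |

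None of these gives 52. In the schedule, Week 52 is a visit, a dosing time and a database lock; it is not the end of dosing, completion or follow-up.

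**Size of the shortfall, counted from Week 0.**

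- Against last dose and completion: 60 − 52 = 8 weeks; 8/60 = 13%.
- Against the last visit: 84 − 52 = 32 weeks; 32/84 = 38%.

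**Doses outside the window.** Active doses in Groups I and II fall at Weeks 0 and 4, then every 8 weeks from Week 12: 0, 4, 12, 20, 28, 36, 44, 52, 60. Only Week 60 comes after Week 52. The same holds in Group III (16, 20, 28, 36, 44, 52, 60).

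**Sensitivity to the starting point.** The criterion does not say when its 52 weeks begin. If they begin at a screening visit 6 weeks before Week 0, they end at Week 52 − 6 = 46. The Week 52 dose would then also lie outside.

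**Primary endpoint.** Week 16 is inside the stated window from either starting point.

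**The case against.** The strongest reply is that the operative words of criterion 18 already exclude surgery planned at any time during expected participation, so a careful investigator would not be misled. There are also backstops. Criterion 38 lets the investigator exclude anyone with a condition that could interfere with the protocol's assessments, and section 4 tells investigators to take questions about the criteria to the sponsor. This stands in part. A reader might infer that subjects with surgery planned after Week 52 are simply eligible and will be enrolled. The document does not establish that; it gives two conflicting answers. But the backstops are discretionary and do not make the criterion consistent.

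A second reply is that 52 weeks may be a chosen horizon, since section 3.2 speaks of evaluating the two doses over one year and a database lock falls at Week 52. That may be where the number came from. Section 3.2 describes dose evaluation, however, while criterion 18 offers the number as the duration of participation.

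A third reply is that little is at risk after Week 60: dosing has ended, the subject counts as a completer, and section 8.2 lifts all limits on concomitant therapy. The Week 72 and 84 data are thus already open to other influences, including new treatment for the disease. This stands. It is why 38% should be read as the upper end of the range and not as the size of the problem.

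**Conclusion.** The contradiction is real but minor. The 52-week figure agrees neither with the criterion's own words nor with sections 3.1 and 10.1. The gap is 8 weeks (13% of 60) if participation is taken to end at last dose and completion, and 32 weeks (38% of 84) if it ends at the last visit. Both figures assume that the 52 weeks run from Week 0.

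The consequence is conflicting eligibility for a subject who, at screening, already has surgery not under local anesthesia planned more than a year ahead. Few subjects are likely to fit that description, although the protocol gives no figure. A reader might also infer that the last two doses are exposed; counted from Week 0, only the Week 60 dose is. Nor does the point reach the main efficacy conclusions: the primary and major secondary endpoints are at Week 16, well inside the window. What remains is an operative eligibility figure that is wrong as written and easy to correct.

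**What to change.** Reconcile criterion 18 with sections 3.1 and 10.1. Either correct the figure, or delete the parenthesis so that the words govern. In both cases state the start and end of the window. Deletion alone would leave expected participation open to two readings, because section 10.1 places completion at Week 60 and section 3.1 places the last visit at Week 84. Which window applies is the sponsor's decision, and the documents do not settle it.

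The cost is one phrase in one criterion, and possibly a few more screen failures. If enrolment has already closed, which the protocol does not say, the useful step is to check whether any enrolled subject had surgery planned after Week 52 and to record how the criterion was applied.
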